1.3. Schedule of Activities for Part A and Part B

																			Follo	ow-up ^b
Procedures	Screen Treatment Period (weeks) ^a												ı	Ī	ı		8 weeks after last dose	14 weeks after last dose/EOS		
	≤ 28 d prior to d1	0 (d1)	1	2	3ª	4	8	12	13ª	14	15ª	16	17ª	18	20	24	28	32 or ET ^p	39	45
Informed consent	X																			
Eligibility criteria	X	X																		
Hurley staging	X	X										X								
Demography	X																			
Physical exam	X																	X		
Weight	X	X																		
Height	X																			
Medical and medication history	X	X																		
Alcohol and nicotine use	X																			
Vital signs ^c	X	X	X	X	X	X	X	X	X	X	X	X	X	X	X	X	X	X	X	
12-lead ECG ^d	X											X						X	X	
Chest X-ray ^e	X																			
C-SSRS	X	X				X	X	X				X			X	X	X	X	X	
AE reporting ^f (through 4 weeks after last dose)		_																	-	
SAE reporting ^f (through 8 weeks after last dose)	X	_																	—	

																			Follo	ow-up ^b
Procedures	Screen		Treatment Period (weeks) ^a												8 weeks after last dose	14 weeks after last dose/EOS				
	≤ 28 d prior to d1	0 (d1)	1	2	3ª	4	8	12	13ª	14	15ª	16	17ª	18	20	24	28	32 or ET ^p	39	45
Prior & Concomitant medication ^g	Х	_																	-	
Efficacy Assessments																				
Lesion count ^h	X	X				X	X	X				X				X	X	X		
NRS Patient Glob. Ass. Skin Pain ⁱ	X	_										•	X	X		X	X	X		
PGA		X				X	X	X				X				X	X	X		
Erythema score		X				X	X	X				X				X	X	X		
Photography (opt. substudy) ^j		X					X					X						X		
HS-PGIC		X				X	X	X				X				X	X	X		
HADS	X	X	X	X	X	X	X	X	X	X	X	X	X	X	X	X	X	X	X	
DLQI		X					X					X				X		X		
EQ-5D		X					X					X				X		X		
SF-12		X					X					X				X		X		
Laboratory Tests																				
Serology (HBsAg, HCV)	X																			
TB test ^k	X																			
HIV testing	X																			
Hematology/Chemistry	X	X				X	X	X				X				X		X	X	

																			Follo	ow-up ^b
Procedures	Screen		Treatment Period (weeks) ^a												8 weeks after last dose	14 weeks after last dose/EOS				
	≤ 28 d prior to d1	0 (d1)	1	2	3ª	4	8	12	13ª	14	15ª	16	17ª	18	20	24	28	32 or ET ^p	39	45
Urinalysis	X	X					X	X				X						X	X	
C-reactive protein	X	X				X	X	X				X				X		X		
Fasting lipid (total cholesterol, triglycerides & HDL)	X											X								X
Hemoglobin A1C		X										X						X		
Pregnancy test (WOCBP only) ¹	X	X				X	X	X				X			X	X	X	X	X	
PK sampling ^m		X		X		X	X	X				X				X		X	X	X
ADA sampling ^m		X		X		X	X	X				X				X		X	X	X

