- ^c Vital signs include measurements of temperature, respiratory rate, systolic and diastolic blood pressure, and pulse. Measurements should be taken in a sitting position after 5 minutes of rest.
- d Electrocardiograms in triplicate will be recorded after subject has been supine for at least 5 minutes.
- ^e Chest x-ray (posterior/anterior or anterior/posterior) will be performed at screening for subjects who do not have a chest x-ray available within 3 months of screening. Women of childbearing potential must have negative pregnancy test before x-ray is performed.
- f Serious adverse events will be recorded from the signing of informed consent through the 8-week follow-up visit (ie, 8 weeks after the last dose of study drug); adverse events will be recorded from Day 1 (ie, administration of study drug) until 4 weeks after the last dose of study drug.
- ^g Confirm ongoing antiseptic wash requirement at every visit. From Screening through Week 16, subjects will complete a daily diary of their analgesic use. From Week 16 through Week 32, subjects will be required to tell site staff if they took any analgesics within 24 hours of their site visit. See Section 10.10. Subjects will refrain from taking analgesics 12 hours before the site visit, if possible.
- ^h Lesion count will be performed at every study visit marked in the Schedule of Activities and must address all relevant anatomical regions in each subject. The AN count includes counts of draining tunnels (fistulas and sinuses). See Section 8.1.1 for more details. Any unscheduled visit for disease worsening based on the investigator judgment will include AN count and will be recorded in the appropriate CRF.
- ¹From screening through Week 16, subjects will complete a daily diary of their skin pain. See Section 8.1.5. No in-site assessment of skin pain will be completed at the Week 16 visit. From Week 16 through Week 32, subjects will complete skin pain assessments at the site. Note: subjects may not be randomized if pain diaries are not completed for ≥ 3 out of 7 days (at a minimum) prior to the Day 1 visit.
- ^j For subjects who consent to the optional photography substudy at selected sites, photographs will be taken.
- ^k QuantiFERON® test or PPD test for TB will be performed. Note: T-SPOT® testing may be allowed after consultation with medical monitor.
- ¹Serum pregnancy test required for screening and urine pregnancy test required at all other times for women of childbearing potential.

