8.1.3. Hurley Stage

The Hurley Stage is a severity classification for HS that was developed in 1989 and is widely used for the determination of the severity of HS (Hurley, 1989). The Hurley Stage is defined by the following criteria:

- Stage I: Abscess formation, single or multiple, without sinus tracts and cicatrization (scarring).
- Stage II: Recurrent abscesses with tract formation and cicatrization, single or multiple, widely separated lesions.
- Stage III: Diffuse or near-diffuse involvement, or multiple interconnected tracts and abscesses across the entire area.

The study investigator will determine the Hurley Stage in each affected anatomical region at the designated study visits listed in the SoA (Section 1.3). If more than one stage is present in a region, the worst state in each region should be entered.

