2.6. Exploratory Efficacy Variables

The exploratory efficacy variables for Part B are:

- HiSCR75 at Weeks 2, 4, 8, 12, and 32
- HiSCR90 at Weeks 2, 4, 8, 12, and 32
- HiSCR100 at Weeks 2, 4, 8, 12, and 32
- HiSCR50 at Weeks 2, 4, 8, 12 and 32

- Achieving AN count of 0, 1, or 2 at Weeks 4, 8, 12, 24, and 32 among subjects with baseline Hurley Stage II
- Change in PGA of Skin Pain (at its worst and average respectively) from baseline at Weeks 4, 8, 12, 16, 24, and 32
- Modified Sartorius Score after Weeks 4, 8, 12, 16, 24, and 32 (see Appendix for scoring method)
- HS flares through Weeks 4 and 32
- IHS4 scores at Weeks 4, 8, 12, 16, 24, and 32, where IHS4 is defined as: IHS4 score (points) = (number of inflammatory nodules × 1) + (number of abscesses × 2) + (number of draining tunnels [fistulae/sinuses] × 4)
- IHS4-55 response rates at Weeks 4, 8, 12, 16, 24 and 32, where IHS4-55 is defined as a decrease in IHS4 of 55% or more from baseline
- Change from baseline to Week 16 in HS-PGA
- Change from baseline to Week 16 in EQ-5D (see Appendix for scoring method)
- Change from baseline to Week 16 in DLQI (see Appendix for scoring method)
- Change from baseline to Week 16 in HADS, HADS-anxiety, and HADS-depression (see Appendix for scoring method)
- Trough plasma concentrations of izokibep at collected timepoints (baseline, Week 4, 8, 12, 16, 24, 32, 39, and 45)

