Appendix 1: Document History

Appendix 2: End Points Definitions and Scoring Method Modified Sartorius Score⁸

The modified Sartorius score includes an assessment of the anatomical regions involved, the numbers and scores of lesions for each region, the longest distance between 2 relevant regions (or size of a single lesion), and whether all lesions are separated by normal skin (yes or no). The detailed scoring is as following:

Each region will score as:

Item No	Items	Scoring Rules	Points	Score:
1	Anatomical region	If the region is affected	3	
		If the region is not affected, the score for that region is 0, and no further calculations are needed for the region. If the region is affected, the following are added in addition to the 3 points for the region in line 1 above.		
	For each affected region:			
2	Nodules (Inflammatory)	Count from this region	1	$1 \times \text{count}$
3	Fistulae (Draining only)	Count from this region	6	$6 \times \text{count}$

4	Longest distance between two relevant lesions within a region or size of the lesion if single	< 5 cm	1	
		5 - 10 cm	3	
		> 10 cm	9	
5	Lesions separated by normal skin?*	Yes	0	
		No	9	
	Score for the region			Sum of above

* If Lesions separated by normal skin = "No" and/or Hurley Stage = "STAGE III" then 9 points is added for the region.

Score for each region is (if the region involved) = $3 + (number of inflammatory nodule) \times 1$ + {(number of draining fistula) × 6 + {0 < (The longest distance between two relevant lesions [or size of lesion if single]) <5} × 1+ {5≤(The longest distance between two relevant lesions [or size of lesion if single]) ≤ 10} × 3 + {(The longest distance between two relevant lesions [or size of lesion if single]) > 10} × 9 + (all lesions separated by normal skin = Yes or Hurley Stage = "STAGE III") × 9

Modified Sartorius score is the sum of the score of each region. Any region with no involvement will have a score of zero for purposes of calculating the modified Sartorius score.

A region is considered "affected" if any of the following conditions are true:

- Abscess Count > 0 OR
- Any "Interventions needed" questions response = YES
- Any "Interventions needed DATE" question is not missing.
- Any "How many lesions had intervention" question > 0
- Any "How many lesions had intervention AND are no longer present" > 0
- Non-draining fistula count > 0
- Draining fistula count > 0
- Non-inflammatory nodule count > 0

- Inflammatory nodule count > 0
- Hypertrophic scar > 0

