- Longest distance > 0
- Normal appearance tissue = NO Hurley Stage contains "STAGE"

EQ-5D⁹

The EQ-5D descriptive system comprises the following 5 dimensions: mobility, self-care, usual activities, pain/discomfort, and anxiety/depression. Each dimension has 3 levels: no problems, some problems, and extreme problems. A unique health state is defined by combining 1 level from each of the 5 dimensions. There are 243 possible health states defined in this way. Each state is referred to in terms of a 5-digit code. No health state value will be calculated if any of the dimensions are missing.

Domain Scores of EQ-5D-3L Descriptive System

Response Category	Score
No problems	1
Moderate problems	2
Severe problems	3

Note: Missing values are coded as '.'. Ambiguous values (e.g., 2 boxes are ticked for a single dimension) should be treated as missing values.

EQ-5D-3L = sum(non-missing question score)/(number of non-missing questions) \times 5. If the number of questions with a missing answer is \geq 3 (\geq 50%) then EQ-5D-3L is missing.

For example, if a patient provides the following responses: Mobility = No problems, Self-care = No problems, Usual Activities = Moderate problems, Pain/Discomfort = Moderate problems, Anxiety/Depression = Extreme problems, his response sequence is 11223. The 243 theoretical possible sequences can then be mapped to an index value to provide a summary across all dimensions. For the calculation of the index value, the UK value set based on Time Trade-Off method will be used. The scoring algorithm is as follows:

Full health (11111) =	1.000
At least one domain at 2 or 3 (N2): At least one domain at 3 (N3):	-0.081 -0.269
Mobility level 1:	0

Mobility level 2:	-0.069
Mobility level 3:	-0.314
Self-care level 1:	0
Self-care level 2:	-0.104
Self-care level 3:	-0.214
Usual activities 1:	0
Usual activities 2:	-0.036
Usual activities 3:	-0.094
Pain/discomfort 1:	0
Pain/discomfort 2:	-0.123
Pain/discomfort 3:	-0.386
Anxiety/depression 1:	0
Anxiety/depression 2:	-0.071
Anxiety depression 3:	-0.236

The index for the patient with example sequence 11223 = 0.255, calculated as follows:

Full health = 1

Minus N2: -0.081

Minus N3: -0.269

Minus mobility level 1:0

Minus self-care level 1:0

Minus usual activities level 2: -0.036

Minus pain/discomfort level 2: -0.123

Minus anxiety/depression level 3: -0.236

where level 1 corresponds to no problems, level 2 to some problems and level 3 to extreme problems.

DLQI¹⁰

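### The modified Sartorius score uses regional Hurley Stage, scheduled after baseline only at Week 16, so a literal reading can lower the score at Weeks 4, 8, 12, 24 and 32 with no change in the skin

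*SAP*

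**What the plan says.** **The score.** SAP Appendix 2 scores each region and sums over regions. Hurley Stage enters twice.

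- The normal-skin item carries the footnote "If Lesions separated by normal skin = 'No' and/or Hurley Stage = 'STAGE III' then 9 points is added for the region".
- The list of conditions that make a region affected (3 points, and the gateway to all other points) ends with "Hurley Stage contains 'STAGE". In the extracted text this line runs on from the preceding item, so treating it as a separate condition is a reading.

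**When stage is collected.** Protocol 1.3 has the row "Hurley staging X X X", with the marks under Screening, Day 1 and Week 16. Protocol 8.1.3 says the investigator "will determine the Hurley Stage in each affected anatomical region at the designated study visits listed in the SoA".

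**When the score is used.** SAP 2.6 lists "Modified Sartorius Score after Weeks 4, 8, 12, 16, 24, and 32". SAP 6.6.5 analyses change from baseline up to Week 16 with an MMRM, p-values and line plots. SAP 6.6.7 fits descriptive Day 1 to Week 32 models by randomized group. It repeats them, with line plots, in placebo subjects who started izokibep in Period 2 and still met the lesion criteria at Week 16.

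**Protocol definition.** Protocol 8.1.1.3 describes the score through regions involved, lesion numbers, longest distance and separation by normal skin. Hurley Stage is not among its inputs.

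**The concern.** One input to the score has no scheduled value at five of the six post-baseline timepoints. Both Hurley clauses are true/false tests, and a blank fails both. The same skin can therefore score lower at Weeks 4, 8, 12, 24 and 32 than at Day 1 or Week 16.

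Appendix 2 gives missing-item rules for the EQ-5D, DLQI, HADS, erythema score and SF-12, but none for the modified Sartorius score. SAP 6.6 presents continuous endpoints without imputation.

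At stake is the shape of the curve: a false fall at Weeks 4 to 12, recovery at Week 16, and a second false fall at Weeks 24 and 32. In the placebo-only summary of SAP 6.6.7 the second fall would begin just as izokibep starts, and that summary has no continuously treated comparator.

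**Working it through.** No stated figure in the plan bears on this point, so there is nothing to reproduce first. The check sets the schedule against the scoring rule and then scores one region with and without a recorded stage.

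**Schedule (protocol 1.3)**

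- Hurley staging: Screening, Day 1, Week 16.
- Lesion count: Screening, Day 1, Weeks 4, 8, 12, 16, 24, 28, 32.
- Score analysed: Weeks 4, 8, 12, 16, 24, 32. Stage is unscheduled at five of these six.

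**Regional score (SAP Appendix 2)**

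Score = 3 (if affected) + 1 × inflammatory nodules + 6 × draining fistulas + distance points (1, 3 or 9) + 9 if the normal-skin/Stage III condition is met.

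**Active example region:** 2 inflammatory nodules, 1 draining fistula, 6 cm. Without the 9-point item the score is 3 + 2 + 6 + 3 = 14; with it, 23. A blank is treated as not Stage III.

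| Rule | Stage | Separated by normal skin | Stage recorded | Stage blank | Loss |
|---|---|---|---|---|---|
| Footnote | III | Yes | 23 | 14 | 9 |
| Footnote | III | No | 23 | 23 | 0 |
| Footnote | I or II | Yes | 14 | 14 | 0 |
| Footnote | I or II | No | 23 | 23 | 0 |
| Printed formula | III | No | 23 | 14 | 9 |
| Printed formula | III | Yes | 23 | 23 | 0 |

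The last two rows are needed because the formula printed under the scoring table awards the 9 points when the separation answer is Yes, while the table and footnote award them for No. Which Stage III regions are exposed depends on which of the two is programmed.

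**Region affected only through its Hurley entry** (no other finding, separation item unanswered): Stage I or II falls from 3 to 0; Stage III falls from 3 + 9 = 12 to 0.

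**Average effect.** The documents do not give the share of exposed regions, so it has to be assumed. With share q of subjects having m exposed active regions, the mean shift is 9 × q × m.

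| q | m = 1 | m = 2 |
|---|---|---|
| 0% | 0 | 0 |
| 10% | 0.9 | 1.8 |
| 25% | 2.25 | 4.5 |
| 50% | 4.5 | 9.0 |

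For scale, one draining fistula scores 6 points.

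**Week 16.** Stage is scheduled at both Day 1 and Week 16, so both scores use the same inputs and missing staging does not affect that change.

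**After the fix.** With stage removed from the score, or recorded at every lesion count, the artificial change is 0 at every visit when true status is unchanged.

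**The case against.** **The loss is conditional.** It needs a blank to be programmed as not Stage III or not affected, which the SAP does not say. Carrying the last stage forward, or setting the score to missing, gives no artificial fall. This stands. Neither alternative is written down, however: carry-forward would hold Day 1 points through Week 12 even in regions that clear, and missing scores would empty five of six planned timepoints.

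**Stage may be recorded more often than scheduled.** Under the erythema score, Appendix 2 names a combined Lesion Count/Hurley Stage eCRF form and counts a region as affected unless its stage is not applicable. That rule works better if stage is entered whenever the form is. Without the CRF this cannot be settled. Against it, the lesion-count form in protocol 10.7 has no Hurley column, and a blank would pass the erythema test but fail the Sartorius test.

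**Exposed regions may be few.** Protocol 8.1.3 defines Stage III by diffuse or interconnected disease, which would usually be answered as not separated; under the footnote such regions keep their 9 points. Scars, fistulas, distance and past interventions also make a region affected without Hurley. Both points stand and limit the likely size. But the footnote's Stage III clause changes a score only when the separation answer is not No, and under the printed formula the usual Stage III answer is the exposed one.

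**Stronger readings a reader might infer.**

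- *The score certainly drops.* The documents leave the handling of blanks open.
- *The fall is specific to subjects who switch from placebo.* The same mechanism acts on continuing izokibep groups, which SAP 6.6.7 also reports by randomized group, and on all groups at Weeks 4 to 12.
- *The arm with more clearing is penalised at Week 16.* This assumes that cleared regions keep Stage III, but stage is reassessed at Week 16 and the documents do not say how cleared regions are staged.

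**Conclusion.** The mismatch is real: the scoring rule tests regional Hurley Stage at visits where the protocol does not schedule it. Applied literally with blank stages and the footnote, a Stage III region marked as separated loses 9 points. A region affected only through Hurley loses 3 points (Stage I or II) or 12 (Stage III). These losses fall at Weeks 4, 8, 12, 24 and 32 with no clinical change.

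Change from baseline at those visits, and the Week 16 to Week 24 and 32 trajectories, could then show false improvement in all groups. The placebo-only switch summary is the most exposed to misreading.

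The conclusion rests on three assumptions: blanks fail both tests, stage is not in fact recorded off schedule, and the run-together Hurley line is a separate condition (this last matters only for the 3- and 12-point cases). The average size is unknown.

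The endpoint is exploratory and the post-Week 16 models are descriptive. The Week 16 change from baseline and every primary and secondary result are unaffected. It should still be corrected before the score is derived.

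**What to change.** - Remove both Hurley clauses from the modified Sartorius section of Appendix 2. Award the 9 points only when intervening normal tissue is answered No, and define an affected region from the lesion, scar, distance and intervention fields. Every visit is then scored only from items collected at each lesion count, as protocol 8.1.1.3 describes.
- Reconcile the footnote and scoring table with the printed formula. This is needed whatever is decided about Hurley Stage.
- First check the eCRF. If it does record stage at every lesion count, correct the Schedule of Activities and protocol 8.1.3 instead.

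Restricting the analysis to Day 1 and Week 16 is not recommended, because it would discard timepoints listed in protocol section 3.

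The cost of the main change is appendix wording and one derivation program, with no new data. The alternative is a correction to two places in the protocol.
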